**Table 2 - Pembrolizumab infusion-related reaction dose modification and treatment guidelines**

| NCI CTCAE Grade   | Treatment   | Premedication at subsequent dosing   |
|---|---|--|
| Grade 1
Mild transient reaction; infusion interruption not indicated; intervention not indicated  | Increase monitoring of vital signs as medically indicated until the participant is deemed medically stable in the opinion of the investigator.  | None   |
| Grade 2
Therapy or infusion interruption indicated but responds promptly to symptomatic treatment (eg, antihistamines, NSAIDs, narcotics, IV fluids); prophylactic medications indicated for ≤24 hrs. | Stop Infusion.
Additional appropriate medical therapy may include but is not limited to: 
 
• IV fluids,
 
• Antihistamines,
 
• NSAIDs,
 
• Acetaminophen,
 
• Narcotics.
 
 Increase monitoring of vital signs as medically indicated until the participant is deemed medically stable in the opinion of the investigator.
If symptoms resolve within 1 hour of stopping drug infusion, the infusion may be restarted at 50% of the original infusion rate (eg, from 100 mL/hr. to 50 mL/hr.). Otherwise dosing will be held until symptoms resolve and the participant should be premedicated for the next scheduled dose.
Participants who develop Grade 2 toxicity despite adequate premedication should be permanently discontinued from further study drug treatment | Participant may be premedicated 1.5 h (±30 minutes) prior to infusion of pembrolizumab with:
Diphenhydramine 50 mg po (or equivalent dose of antihistamine).
Acetaminophen 500-1000 mg po (or equivalent dose of analgesic). |

| NCI CTCAE Grade  | Treatment  | Premedication at subsequent dosing |
|--|--|------------------------------------|
| Grades 3 or 4   | 
 
• Stop Infusion.
 
   | No subsequent dosing               |
| Grade 3:
Prolonged (ie, not rapidly responsive to symptomatic medication and/or brief interruption of infusion); recurrence of symptoms following initial improvement; hospitalization indicated for other clinical sequelae (eg, renal impairment, pulmonary infiltrates) | Additional appropriate medical therapy may include but is not limited to: 
 
• Epinephrine*,
 
• IV fluids,
 
• Antihistamines,
 
• NSAIDs,
 
• Acetaminophen,
 
• Narcotics,
 
• Oxygen,
 
• Pressors,
 
• Corticosteroids.
 
  |                                    |
| Grade 4:
Life-threatening; urgent intervention indicated   | Increase monitoring of vital signs as medically indicated until the participant is deemed medically stable in the opinion of the investigator. 
 
• Hospitalization may be indicated.
 
 *In cases of anaphylaxis, epinephrine should be used immediately.
Participant is permanently discontinued from further study drug treatment. |                                    |

Appropriate resuscitation equipment should be available at the bedside and a physician readily available during the period of drug administration.

**Table 3 - SAR444245 Infusion-related reaction dose modification and treatment guidelines**

| NCI CTCAE Grade   | Treatment   |
|---|---|
| Grade 1
Mild transient reaction; infusion interruption not indicated; intervention not indicated  | If IRR happens during infusion, continuation of SAR444245 a infusion is per Investigator's judgment following close direct monitoring of the participant's clinical status.
SAR444245 infusion may be interrupted at any time if deemed necessary.
If interrupted, IRR will be classified as Grade 2 as per NCI-CTCAE definition.
If IRR happens after completion of infusion, increase monitoring of vital signs as medically indicated until the participant is deemed medically stable in the opinion of the investigator.   |
| Grade 2
Therapy or infusion interruption indicated but responds promptly to symptomatic treatment (eg, antihistamines, NSAIDs, narcotics, IV fluids); prophylactic medications indicated for ≤24 hrs. | Interrupt SAR444245 infusion.
If symptoms resolve within 1 hour of interrupting drug infusion, the infusion may be restarted at 50% of the original infusion rate. Otherwise dosing will be held until symptoms resolve and the participant will be premedicated for the next scheduled dose according to Section 6.1.2.1 of the master protocol.
Give the next infusion at half the infusion rate.
During or after completion of infusion, additional appropriate medical therapy may include but not limited to IV fluids, antihistamines, NSAIDs, acetaminophen, narcotics.
Increase monitoring of vital signs will be as medically indicated until the participant recovers. |

| NCI CTCAE Grade   | Treatment  |
|---|--|
| 
Grade 3
Prolonged (ie, not rapidly responsive to symptomatic medication and/or brief interruption of infusion); recurrence of symptoms following initial improvement; hospitalization indicated for other clinical sequelae
 | 
Permanently discontinue SAR444245. The participant can continue treatment with the other anti-cancer therapy in combination
During or after completion of infusion, additional appropriate medical therapy may include but is not limited to epinephrineb, IV fluids, antihistamines, NSAIDs, acetaminophen, narcotics, oxygen, vasopressors, corticosteroids.
Increase monitoring of vital signs as medically indicated until the participant recovers.
  |
| 
Grade 4
Life-threatening; urgent intervention indicated
   | 
Permanently discontinue SAR444245. The participant can continue treatment with the other anti-cancer therapy in combination.
During or after completion of infusion, additional appropriate medical therapy may include but is not limited to epinephrineb, IV fluids, antihistamines, NSAIDs, acetaminophen, narcotics, oxygen, vasopressors, corticosteroids.
Increase monitoring of vital signs as medically indicated until the participant recovers.
 |

a Information for preparation and storage of SAR444245 are provided in the pharmacy manual.

b In cases of anaphylaxis, epinephrine should be used immediately

Abbreviations: CTCAE = Common terminology criteria for adverse events; IRR = Infusion-related reaction; NCI = National Cancer Institute; NSAIDs: nonsteroidal anti-inflammatory drugs.

#### 6.5.4.2 Anaphylaxis

Anaphylaxis should lead to immediate interruption of ongoing infusion, and to permanent discontinuation of SAR444245 being administered.

Management should be prompt and may include but is not limited to administration of epinephrine, IV fluids, antihistamines, oxygen, vasopressors, corticosteroids, as well as increased monitoring of vital signs as medically indicated, until the participant recovers (see guidelines) (26, 27, 28).

#### 6.5.4.3 Fever, flu-like symptoms and cytokine-release syndrome (CRS)

Fever can frequently happen with infusion of IL-2 and may possibly evolve into flu-like symptoms or could be an early manifestation of CRS. Fever or flu-like symptoms should be graded according to CTCAE V5.0 and managed according to institutional standards.

Monitoring of vital signs is detailed in Safety Assessments (Section 8.2.2).

Cytokine-release syndrome should be graded as per American Society for Transplantation and Cellular Therapy (ASTCT) criteria integrated with central laboratory cytokine results, and managed per guidelines in Table 4. If any grade of CRS is suspected, sites should make every effort to draw an additional blood sample for cytokines levels (by central laboratory) prior to the administration of tocilizumab or alternative therapies per site practice in CRS management, as well as C-reactive protein (CRP) and ferritin (by local laboratory).

Sites should have at least 2 full doses of tocilizumab or alternative therapies per site practice in CRS management available and access to an intensive care unit (ICU), in case participants develop CRS.

Guidelines for management of CRS according to severity grading are provided in [Table 4](#).  
ASTCT CRS consensus grading scale is provided in Section 10.13 of the master protocol.

**Table 4 - Guidelines for the management of suspected cytokine release syndrome (CRS)**

| Event severity (ASTCT CRS Consensus Grading)  | Recommended SAR444245 dose modification and supportive care guidelines   |
|---|--|
| 
Grade 1
 
 
• Fever (Temperature <math>\geq 38^{\circ}\text{C}</math>)b
 
• No hypotension
 
• No hypoxia
 
   | 
No dose modification of SAR444245a
 
Appropriate symptomatic treatment may include but is not limited to IV fluids (care should be taken to not excessively hydrate if evidence of vascular leak), antihistamines, NSAIDs and acetaminophen.
 
Close direct monitoring of the participant's clinical status. Clinical and laboratory monitoring should initially be performed daily, then less frequently as the participant improves.
  |
| 
Grade 2
 
 
• Feverb (Temperature <math>\geq 38^{\circ}\text{C}</math>)
 
• Hypotension not requiring vasopressors
 
• and/orc hypoxia requiring low-flow nasal cannulad or blow-by.
 
  | 
Temporarily interrupt SAR444245 if event occurs during infusion
 
Additional appropriate medical therapy may include but is not limited to IV fluids (care should be taken to not excessively hydrate if evidence of vascular leak), antihistamines, NSAIDs and acetaminophen.
 
Increase monitoring of vital signs, cardiac and other organ functions closely as medically indicated until the participant recovers. Transfer to ICU may be required.
 
For participants with comorbidities, older age, or with oxygen requirement, hypotension, or participants in whom symptoms (eg, high grade fever) that do not respond to antipyretics within 72 hours treatment with corticosteroids and/or tocilizumab or alternative therapies per site practice in CRS management should be considered, as per guidance for Grade 3 events.
 
IMP may be resumed when clinical symptoms have resolved or improved to Grade 1 and corticosteroid taper. No dose modification is required but decreasing to half the infusion rate can be considered.
 |
| 
Grade 3
 
 
• Feverb (Temperature <math>\geq 38^{\circ}\text{C}</math>)
 
• Hypotension requiring a vasopressor with or without vasopressin
 
• And/orc hypoxia requiring high-flow nasal cannulad, face mask, nonrebreather mask, or Venturi mask
 
  | 
If CRS grade 3, temporarily cycle delay SAR444245, and resume subsequent treatment only when symptoms have resolved or improved to Grade 1.
 
SAR444245 can be either restarted at ■ <math>\mu\text{g}/\text{kg}</math> or permanently discontinued, as clinically indicated.
  |
| 
Grade 4
 
Life-threatening consequences; urgent intervention indicated
 
 
• Feverb (Temperature <math>\geq 38^{\circ}\text{C}</math>)
 
• Hypotension requiring multiple vasopressors (excluding vasopressin)
 
• And/orc hypoxia requiring positive pressure (eg, CPAP, BiPAP, intubation and mechanical ventilation)
 
 | 
If CRS Grade 4, permanently discontinue SAR444245.
 
If CRS Grade 3 or Grade 4, initiate IV corticosteroids (outside of the context of CAR-T cells, corticosteroids alone maybe initiated in first intention) and tocilizumab or alternative therapies per site practice in CRS management considered, and/or epinephrine and/or other vasopressors should be administered as needed. Participants with severe CRS may require management in intensive care setting, with monitoring of clinical status and laboratory tests performed at least daily.
 
As the participant improves, the intensity of the monitoring and setting can be decreased, but the participant should not be discharged from the hospital until clinically stable. Corticosteroids can then be administered IV or orally every 8 hours for up to 3 days, then tapered over 4 days. In
   |

| Event severity (ASTCT CRS Consensus Grading) | Recommended SAR444245 dose modification and supportive care guidelines  |
|--|---|
|  | 
general, tapering of steroids can start when vasopressors and high-flow oxygen are no longer needed.
 
CRS is considered resolved when there is sustained resolution of fever and there is no longer a need for oxygen supplementation to relieve hypoxia nor vasopressors to maintain blood pressure; however, normalization of temperature alone does not define resolution of CRS.
   |
|  | 
If no clinical improvement in oxygenation, hypotension, fever, and other CRS manifestations is observed within 24 to 72 hours, initiate management for persistent or worsening CRS. Re-evaluation for other contributing conditions will be done, such as infection, cardiac, thromboembolic and other complications. Intravenous Tocilizumab at 8 mg/kg (for participants weighing <math>\geq 30</math> kg) or alternative therapies per site practice in CRS management should be administered, and steroids should be administered concurrently. If still no improvement in oxygenation, hypotension fever and other manifestations is observed after the first dose of tocilizumab, it may be repeated after an interval of at least 8 hours and should not exceed 4 doses in total.
 
For participants with severe CRS who fail to improve after repetitive treatment with both tocilizumab or alternative therapies per site practice in CRS management and steroids, alternative options will be discussed with clinical site specialists
 |

- a Information for preparation and storage of SAR444245 is provided in the pharmacy manual.
- b Fever is defined as temperature  $\geq 38^{\circ}\text{C}$  not attributable to any other cause. In patients who have CRS then receive antipyretic or anticytokine therapy such as tocilizumab or alternative therapies per site practice in CRS management or steroids, fever is no longer required to grade subsequent CRS severity. In this case, CRS grading is driven by hypotension and/or hypoxia.
- c CRS grade is determined by the more severe event: hypotension or hypoxia not attributable to any other cause. For example, a patient with temperature of  $39.5^{\circ}\text{C}$ , hypotension requiring 1 vasopressor, and hypoxia requiring low-flow nasal cannula is classified as Grade 3 CRS.
- d Low-flow nasal cannula is defined as oxygen delivered at  $\leq 6$  L/minute. Low flow also includes blow-by oxygen delivery, sometimes used in pediatrics. High-flow nasal cannula is defined as oxygen delivered at  $>6$  L/minute.

Abbreviations: AE = Adverse event; ASTCT=American Society for Transplantation and Cellular Therapy; BiPAP= Bilevel Positive Airway Pressure; CPAP= Continuous Positive Airway Pressure; CRS= cytokine release syndrome; ICU=intensive care unit; IL = Interleukin; IMP=investigational medicinal product; IV = Intravenous; NSAIDs=Non-steroidal anti-inflammatory drugs.

#### 6.5.4.4 Immune-related adverse events

AEs associated with pembrolizumab exposure may represent an immunologic etiology. These irAEs may occur shortly after the first dose or several months after the last dose of pembrolizumab treatment and may affect more than one body system simultaneously. Immune-related AEs (irAEs) are thought to be caused by unrestrained cellular immune responses directed at the normal host tissues. Therefore, early recognition and initiation of treatment is critical to reduce complications. Based on existing pembrolizumab clinical study data, most irAEs were reversible and could be managed with interruptions of pembrolizumab, administration of corticosteroids and/or other supportive care.

Investigators must be extremely vigilant and be ready to intervene early in the management of irAEs because the onset of symptoms of irAEs (eg, pneumonitis) may be subtle. For suspected irAEs, adequate evaluation should be performed to confirm etiology or exclude neoplastic, infectious, metabolic, toxin, or other etiologic causes. Additional procedures or tests such as bronchoscopy, endoscopy, skin biopsy may be included as part of the evaluation. Based on the severity of irAEs, withhold or permanently discontinue pembrolizumab and/or SAR444245 and administer corticosteroids.

SAR444245 may increase the incidence and severity of these events.

Dose modification and toxicity management guidelines for irAEs are provided in [Table 5](#). Of note, if the AE is considered immune-related, both drugs in the combination should be held according to recommended dose modifications. If a participant experiences several irAEs, the most conservative recommendation should be followed.

The CTCAE V5.0 must be used to grade the severity of AEs.

When pembrolizumab can be restarted, it should be administered at the initial planned dose and schedule as no modification is allowed:

- If the toxicity does not resolve or the criteria for resuming treatment are not met, the participant must be discontinued from all study drugs.
- If the toxicities do resolve and conditions are aligned with what is defined in [Table 5](#) the combination of SAR444245 and pembrolizumab may be restarted at the discretion of the investigator. In these cases where the toxicity is attributed to the combination or to SAR444245 alone, re-initiation of pembrolizumab as a monotherapy may be considered after communication with the Sponsor.

**Table 5 - Dose modification and toxicity management guidelines for immune-related AEs associated with pembrolizumab and SAR444245**

| General instructions:   |                                 |   |   |  |
|---|---------------------------------|---|---|--|
| 
 
1. Treat severe and life-threatening irAEs with IV corticosteroids followed by oral steroids. Begin other immunosuppressive treatment if the irAEs are not controlled by corticosteroids.
 
2. Pembrolizumab and SAR444245 must be permanently discontinued if the irAE does not resolve or the corticosteroid dose is not <math>\leq 10</math> mg/day within 12 weeks of the last pembrolizumab treatment.
 
3. Begin the corticosteroid taper when the irAE is <math>\leq</math> Grade 1 and continue at least 4 weeks.
 
4. If pembrolizumab and SAR444245 have been withheld, pembrolizumab and SAR444245 may be resumed after the irAE decreased to <math>\leq</math> Grade 1 after corticosteroid taper.
 
 |                                 |   |   |  |
| irAEs   | Toxicity grade (CTCAE V5.0)     | Action with pembrolizumab and SAR444245 | Corticosteroid and/or other therapies   | Monitoring and follow-up   |
| Pneumonitis   | Grade 2                         | Withhold a                   | Administer corticosteroids (initial dose of 1 to 2 mg/kg prednisone or equivalent) followed by taper.
Add prophylactic antibiotics for opportunistic infections. | Monitor participants for signs and symptoms of pneumonitis.
Evaluate participants with suspected pneumonitis with radiographic imaging and initiate corticosteroid treatment. |
|   | Recurrent Grade 2, Grade 3 or 4 | Permanently discontinue b    |   |  |

| irAEs  | Toxicity grade (CTCAE V5.0)   | Action with pembrolizumab and SAR444245                         | Corticosteroid and/or other therapies   | Monitoring and follow-up  |
|--|---|---|---|---|
| Diarrhea/Colitis                                 | Grade 2 or 3  | Withhold a   | Administer corticosteroids (initial dose of 1 to 2 mg/kg prednisone or equivalent) followed by taper.   | 
Monitor participants for signs and symptoms of enterocolitis (ie, diarrhea, abdominal pain, blood or mucus in stool with or without fever) and of bowel perforation (ie, peritoneal signs and ileus).
 
Participants with ≥ Grade 2 diarrhea suspecting colitis should consider GI consultation and performing endoscopy to rule out colitis.
 
Participants with diarrhea/colitis should be advised to drink liberal quantities of clear fluids. If sufficient oral fluid intake is not feasible, fluid and electrolytes should be substituted via IV infusion.
 |
|  | Recurrent Grade 3 or Grade 4  | Permanently discontinue b                            |   |   |
| AST or ALT elevation or Increased Bilirubin      | Grade 2 c  | Withhold a   | Administer corticosteroids (initial dose of 0.5 to 1 mg/kg prednisone or equivalent) followed by taper.   | Monitor with liver function tests (consider weekly or more frequently until liver enzyme value returned to baseline or is stable).  |
|  | Grade 3 d or 4 e  | Permanently discontinue b                            | Administer corticosteroids (initial dose of 1 to 2 mg/kg prednisone or equivalent) followed by taper.   |   |
| Type 1 Diabetes Mellitus (T1DM) or Hyperglycemia | New onset T1DM or Grade 3 or 4 hyperglycemia associated with evidence of β-cell failure | Withhold a,f   | 
Initiate insulin replacement therapy for participants with T1DM.
 
Administer antihyperglycemic in participants with hyperglycemia.
 | Monitor participants for hyperglycemia or other signs and symptoms of diabetes.   |
| Hypophysitis                                     | Grade 2   | Withhold a   | Administer corticosteroids and initiate hormonal replacements as clinically indicated.  | Monitor for signs and symptoms of hypophysitis (including hypopituitarism and adrenal insufficiency).   |
|  | Grade 3 or 4  | Withhold a or permanently discontinue b,f |   |   |
| Hyperthyroidism                                  | Grade 2   | Continue  | Treat with nonselective beta-blockers (eg, propranolol) or thionamides as appropriate.  | Monitor for signs and symptoms of thyroid disorders.  |
|  | Grade 3 or 4  | Withhold a or permanently discontinue b,f |   |   |
| Hypothyroidism                                   | Grade 2, 3, or 4  | Continue  | Initiate thyroid replacement hormones (eg, levothyroxine or liothyronine) per standard of care.   | Monitor for signs and symptoms of thyroid disorders.  |

| irAEs   | Toxicity grade (CTCAE V5.0)  | Action with pembrolizumab and SAR444245                              | Corticosteroid and/or other therapies   | Monitoring and follow-up  |
|---|------------------------------|--|---|---|
| Nephritis: grading according to increased creatinine or acute kidney injury | Grade 2                      | Withhold a  | Administer corticosteroids (prednisone 1 to 2 mg/kg or equivalent) followed by taper. | Monitor changes of renal function.  |
|   | Grade 3 or 4                 | Permanently discontinue b                                 |   |   |
| Neurological Toxicities   | Grade 2                      | Withhold a  | Based on severity of AE administer corticosteroids                                    | Ensure adequate evaluation to confirm etiology and/or exclude other causes  |
|   | Grade 3 or 4                 | Permanently discontinue b                                 |   |   |
| Myocarditis   | Grade 2, 3 or 4              | Permanently discontinue b                                 | Based on severity of AE administer corticosteroids.                                   | Ensure adequate evaluation to confirm etiology and/or exclude other causes. |
| Exfoliative Dermatologic Conditions   | Suspected SJS, TEN, or DRESS | Withhold a  | Based on severity of AE administer corticosteroids                                    | Ensure adequate evaluation to confirm etiology and/or exclude other causes  |
|   | Confirmed SJS, TEN, or DRESS | Permanently discontinue b                                 |   |   |
| All Other irAEs   | Persistent Grade 2           | Withhold a  | Based on severity of AE administer corticosteroids.                                   | Ensure adequate evaluation to confirm etiology or exclude other causes.     |
|   | Grade 3                      | Withhold a or discontinue based on the event g |   |   |
|   | Recurrent Grade 3 or Grade 4 | Permanently discontinue b                                 |   |   |

a SAR444245 to be withheld plus pembrolizumab to be withheld corresponds to "cycle delay".

b Permanently discontinuation of full study treatment.

c AST/ALT: >3.0 to 5.0 x ULN if baseline normal; >3.0 to 5.0 x baseline, if baseline abnormal; bilirubin:>1.5 to 3.0 x ULN if baseline normal; >1.5 to 3.0 x baseline if baseline abnormal.

d AST/ALT: >5.0 to 20.0 x ULN, if baseline normal; >5.0 to 20.0 x baseline, if baseline abnormal; bilirubin:>3.0 to 10.0 x ULN if baseline normal; >3.0 to 10.0 x baseline if baseline abnormal.

e AST/ALT: >20.0 x ULN, if baseline normal; >20.0 x baseline, if baseline abnormal; bilirubin: >10.0 x ULN if baseline normal; >10.0 x baseline if baseline abnormal.

f The decision to withhold or permanently discontinue pembrolizumab and SAR444245 is at the discretion of the investigator or treating physician. If control achieved or ≤Grade 2, pembrolizumab and SAR444245 may be resumed.

g Events that require discontinuation include but are not limited to: encephalitis and other clinically important irAEs (eg. vasculitis and sclerosing cholangitis).

AE(s)=adverse event(s); ALT= alanine aminotransferase; AST=aspartate aminotransferase; CTCAE=Common Terminology Criteria for Adverse Events; DRESS=Drug Rash with Eosinophilia and Systemic Symptom; GI=gastrointestinal; IO=immuno-oncology; ir=immune related; IV=intravenous; SJS=Stevens-Johnson Syndrome; T1DM=type 1 diabetes mellitus; TEN=Toxic Epidermal Necrolysis; ULN=upper limit of normal.

Note: Non-irAE will be managed as appropriate, following clinical practice recommendations.

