### 6.5.2 Cycle delay

The treatment window is  $\pm 3$  days for each of the Q3W administrations. A cycle is deemed to have been delayed if the treatment is administered  $\geq 4$  days beyond the theoretical day of Q3W IMP administration. The participant may receive the next dose after recovery from the toxicity as described in Section 6.5.3. After cycle delayed, such participants may be considered for treatment resumption once the toxicity resolves or improves to Grade 1 or baseline.

Participants may have cycle delay, if toxicity occurs and the participant does not recover according to following rules:

- For Q3W IMP administration: If toxicity occurs and the participant does not recover on the day of planned administration, the cycle will be delayed; restart of study IMPs could occur only on the initiation of the subsequent cycle.
- In case of cycle delay for the recovery of toxicity, the following rules should be followed for restart or discontinuation of the treatment:
  - In case of a cycle delay up to 14 days, it is per Investigator's decision to restart the study treatment.
  - After a cycle delay of  $>14$  days and  $\leq 84$  days, it is per Investigator's decision to restart the study treatment, if a clear benefit from treatment is observed and after consultation with the Sponsor.
  - The study treatment must be permanently discontinued if the cycle delay is longer than 84 days.
- Cycle may be delayed for situations other than TEAEs such as medical/surgical events or logistical reasons not related to study therapy. Participants should be placed back on study therapy within 21 days of the scheduled delay, unless otherwise discussed with the Sponsor (for example for national or regional emergencies). The reason for this delay should be documented in the participant's study record.

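### Substudy 01 Table 5 contradicts itself on restarting both drugs in hypophysitis: footnote f allows it at Grade 2, the Grade 2 row and general instruction 4 do not

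*Protocol*

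**What the plan says.** All places are in Substudy 01 unless stated otherwise.

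- **Table 5, hypophysitis, Grade 3 or 4.** The action cell reads "Withhold a or permanently discontinue b,f", where the letters are footnote marks. Footnote f leaves the choice between holding and stopping to the investigator or treating physician and adds: "If control achieved or ≤Grade 2, pembrolizumab and SAR444245 may be resumed".
- **Table 5, hypophysitis, Grade 2.** The cells read "Hypophysitis | Grade 2 | Withhold a". Only footnote a is attached. Treatment for hypophysitis is "Administer corticosteroids and initiate hormonal replacements as clinically indicated".
- **Table 5, general instruction 4.** "If pembrolizumab and SAR444245 have been withheld, pembrolizumab and SAR444245 may be resumed after the irAE decreased to" a level no higher than "Grade 1 after corticosteroid taper". No class of event is excepted.
- **Table 5, footnote a.** Withholding both drugs counts as a cycle delay, which brings in Section 6.5.2.
- **Section 6.5.2.** After a delay, "such participants may be considered for treatment resumption once the toxicity resolves or improves to Grade 1 or baseline". The preceding sentence refers to Section 6.5.3 for recovery.
- **Section 6.5.3.** It sets the same level for Grade 3 or higher treatment-related events, but gives way where the protocol specifies something else.
- **Tie-break rules.** Section 6.5.1 prefers the most conservative adjustment when a participant has several toxicities. Section 6.5.4.4 does the same for several immune-related events.

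**The concern.** Within one table, the same event at the same grade meets opposite instructions. Hypophysitis that has come down to Grade 2 from a higher grade may be re-dosed under footnote f. Hypophysitis seen for the first time at Grade 2 must be held, and under instruction 4 stays held until Grade 1 or lower after taper. The more severe event thus gets the looser restart condition.

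Two immune-activating drugs are involved, and Section 6.5.4.4 itself warns that SAR444245 may make these events more frequent and more severe. More than timing can turn on it. Section 6.5.4.4 requires all study drugs to be stopped if the criteria for resuming are not met, and general instruction 2 requires permanent discontinuation if the event has not resolved within 12 weeks of the last pembrolizumab dose. For hypophysitis that settles at Grade 2, the choice of line can decide whether treatment continues or ends.

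Section 6.5.1 asks for Sponsor consultation before departing from the protocol's dose modifications, yet a site cannot tell whether a restart at Grade 2 is a departure. Sites reading different lines would also produce different counts in the summaries of adverse events leading to dose modification or full discontinuation (master protocol, Section 9.4.3.5).

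**Working it through.** No sample size, error rate or event count is involved. The check takes one participant through every applicable line: Grade 3 hypophysitis, both drugs withheld, now improved to Grade 2.

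| Line | Answer at Grade 2 |
|---|---|
| Table 5, footnote f | Both drugs may resume |
| Table 5, Grade 2 hypophysitis row | Withhold |
| Table 5, general instruction 4 | Not yet: Grade 1 or lower, after taper |
| Section 6.5.2 | Not yet on its own words: Grade 1 or baseline |
| Section 6.5.3 | Not yet, unless another line counts as specifying otherwise |
| Tie-break rules, Sections 6.5.1 and 6.5.4.4 | Do not apply: one event, not several |

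Three of these lines sit in Table 5 and give two answers. Section 6.5.4.4 refers restart back to the conditions in Table 5, so it cannot choose between them.

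The same check on the other rows that carry footnote f:

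- **Hyperthyroidism, Grade 3 falling to Grade 2.** The Grade 2 row says to continue, which agrees with footnote f. Only the general rules differ.
- **Type 1 diabetes or hyperglycemia.** There is no Grade 2 row to contradict footnote f. Again only the general rules differ.

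Instruction 4 also fits these two rows poorly. Its condition includes a corticosteroid taper, but the treatments listed are insulin or antihyperglycemics in one row and beta-blockers or thionamides in the other. The hypophysitis row does prescribe corticosteroids, so there the taper condition applies directly and footnote f is silent on it. The internal contradiction is therefore confined to hypophysitis.

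**The case against.** The strongest defence is that footnote f is a specific endocrine exception and specific rules override general ones. Section 6.5.3 says that it yields to other provisions. Section 6.5.2 refers to 6.5.3 for recovery and can be read as taking over that carve-out. Section 6.5.4.4 makes Table 5, footnotes included, the test for restart. A reader might infer that footnote f clashes with the whole of Sections 6.5.2 and 6.5.3; because of this wording, the documents do not support that. But the defence does not reach instruction 4, which is in the same table and has no yielding language, or the Grade 2 hypophysitis row, which is as specific as the footnote.

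The cut-off may also be deliberate. Master protocol exclusion E 10 bars ongoing Grade 2 or higher events from prior therapy, yet lets in endocrine events up to Grade 2 that need treatment or hormone replacement. That is fair evidence of intent, but the intent is not stated in Table 5.

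One can also read the Grade 2 row as the action on first reaching that grade, and footnote f as the way back after a Grade 3 or 4 hold. This softens the clash between row and footnote. It still leaves the looser condition with the more severe event, and instruction 4 still speaks to every restart after withholding.

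Finally, the wording is permissive. Footnote f says only that the drugs may be resumed, and Section 6.5.3 leaves the final decision to the investigator. That stands: no line compels dosing at Grade 2. It remains true that one line permits what another withholds.

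**Conclusion.** The point holds for hypophysitis, where Table 5 is wrong as written: footnote f, the Grade 2 row and general instruction 4 cannot all be followed, and nothing in the document ranks them. For type 1 diabetes/hyperglycemia and hyperthyroidism there is only a missing statement that footnote f takes precedence over instruction 4.

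A reader might also infer a probability that Cohort A1 will meet the problem. The documents give no rate for it. If one assumed that 0.5% to 3% of participants have Grade 3 or 4 hypophysitis or a qualifying diabetes/hyperglycemia event, 40 × p gives 0.2 to 1.2 participants, and 1 − (1 − p)^40 gives 18% to 70% for at least one. Those figures overstate the hypophysitis conflict. They include diabetes/hyperglycemia events, and the conflict further requires that treatment was not permanently stopped and that the event has improved to exactly Grade 2 and is still there on a dosing day. The true frequency is an unknown fraction of an assumed number, and the finding does not depend on it.

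The situation is rare and the effect on objective response rate is negligible. The reason to act is a contradictory dosing rule that bears on the safety of individual participants.

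**What to change.** Reconcile footnote f, the Grade 2 hypophysitis row and general instruction 4 in Substudy 01 Table 5 so that hypophysitis has a single resumption condition. If footnote f is meant as an exception for endocrine events, say so in instruction 4 and add a cross-reference in Section 6.5.2; this also closes the smaller gap for type 1 diabetes/hyperglycemia and hyperthyroidism. The medical team decides the condition; none is proposed here.

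The cost is a few words at the next amendment, with no change to design, sample size or analysis. Any other substudy that uses the same table should be checked for the same wording; the text of the other substudies was not available for this check.
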